6.0 SAMPLE SIZE

The overall sample size for this study is 60 subjects aged 2 to 21 years. There are two subgroups which will be analyzed separately as outlined in section 5.1. These subgroups are those subjects aged 2 to 4 years and those subjects aged 5 to 21 years.

Adverse events related to delivery of the tube are expected to occur in approximately 4.5% of ears. The width of the 95% confidence intervals will vary between the overall analysis and the analysis of the subgroups. The table below shows the width of the 95% exact confidence intervals for various analyses.

| Subject Group | # of Subjects | # of Ears | 95% Lower Bound (%) | 95% Upper Bound (%) | Confidence Interval Width (%) |
|------------------|------------------|-----------|------------------------|------------------------|-------------------------------------|
| Overall | 60 | 120 | 1.4 | 9.5 | 8.1 |
| Subgroup | 30 | 60 | 1.0 | 13.9 | 12.9 |

The width of the 95% confidence intervals for this endpoint are on a per ear basis. The interval width for the overall analysis is less than 10 percentage points. For the subgroup analysis, the width of the 95% confidence interval is approximately 13 percentage points.

The rate for successful delivery of the tube is expected to be at least 95%. Again, depending on the analysis being done, the width of the exact 95% confidence interval will vary. The table below shows the width of the confidence intervals for the various analyses. These confidence intervals and widths are based on a per ear basis.

| Subject Group | # of Subjects | # of Ears | 95% Lower Bound (%) | 95% Upper Bound (%) | Confidence Interval Width (%) |
|------------------|------------------|-----------|------------------------|------------------------|-------------------------------------|
| Overall | 60 | 120 | 89.4 | 98.1 | 8.7 |
| Subgroup | 30 | 60 | 86.1 | 99.0 | 12.9 |

Again, the width of the 95% confidence interval for the overall analysis is less than 10 percentage points and for the subgroup analysis the width is approximately 13 percentage points.

7.0 PATIENT POPULATION

Selection Criteria

Patients considered for this study must meet all of the inclusion criteria in section 7.1 below. However, if they meet any of the exclusion criteria in section 7.2, they will not be eligible to participate in the study.

7.1 Inclusion Criteria

Patients must meet all of the following:

- 1. Scheduled to undergo tympanostomy tube insertion in the clinic.
- 2. Children 2 to 21 years old.
- 3. Signed parental consent and child assent documents as applicable.
- 4. Parent is fluent in English

7.2 Exclusion Criteria

Patients will be excluded should they meet any of the following:

- 1. Any condition that, in the opinion of the investigator, may place the subject at greater risk (e.g., child with developmental delay).
- 2. Anatomy precludes sufficient visualization and access to the tympanic membrane.

8.0 INVESTIGATOR AND SITE TRAINING

This study is a continuation of the multi-site, prospective, treatment-only study of the H-TTS. All investigators participating in this study have been trained according to previous versions of the protocol. No new sites will be added.

9.0 TYMPANOSTOMY PROCEDURE

The tympanostomy procedure will take place in the otolaryngology clinic. Movement in young children will be controlled as appropriate (i.e. swaddling, papoose board). Parents will be informed and must agree to the methods that will be used to control movement for their child prior to the procedure. All patients will have a local (topical) anesthetic of surgeon's choice (i.e. Phenol) applied to the tympanic membrane prior to insertion of the H-TTS into the ear canal. Medical staff may choose to provide additional analgesics (i.e. Tylenol) per clinic standard of care.

Distraction/comfort techniques may be used per clinic standard of care, and may include, but are not limited to:

- Pre-procedure medication (i.e. Tylenol)
- Presence of parent for the procedure
- Use of media/videos during the procedure

10.0 CONSENT

A parental consent document will be used for all children under 18 years of age. Patients over 18 years of age will sign a consent document. In addition, a child assent document will be used for children 7-17 years of age (age range may be site-dependent). Prior to obtaining consent, the study will be explained to the parents and older children by the investigator or appropriate designee. Parents and assenting children must sign the appropriate consent document(s) prior to enrollment. In addition, a video release form will be required for parents to sign to give permission for the procedure to be audio and video recorded for patient tolerability assessments.

Additionally, personal health information created or received for the purposes of this study is protected under HIPAA. Patients will be required to sign a HIPAA form allowing the Preceptis Medical, Inc.

Pivotal Clinic Study Protocol Rev 1.5

29 July2020

principal investigator, research staff, and Preceptis access to their individual health information. The site may incorporate the HIPAA form within the consent documents.

The consent documents are located in **Attachment A**.

11.0 STUDY PROCEDURES

11.1 Summary of Study Procedures

The Principal Investigator (PI) is responsible for the quality of all data submitted to Preceptis. Documentation of patient eligibility, procedural experience, first follow up visit (approximately 3-10 weeks after the procedure), and adverse events will be collected. (Sample case report forms are in **Attachment B**)

| CRFs | Type of Form | Timing |
|------|----------------------------------|--|
| #1 | Enrollment | Prior to tympanostomy procedure |
| #1 | Procedure | Time of procedure |
| #2 | AE | As applicable |
| #3 | Parent Survey | Upon completion of procedure and at first follow up visit |
| #4 | Follow Up | First follow up visit after procedure (approximately 3-10 weeks) |
| #5 | Additional Events of Interest | Upon completion of follow up visit |

11.1.1 Baseline

Parents of children who require a tympanostomy tube procedure and meet all study inclusion criteria and none of the exclusion criteria, will be approached for participation in the study by the PI. If the patient and parent agree to participate, the appropriate consent documents will be signed. There are no further baseline tests required for the study.

11.1.2 Procedure

Once appropriate written consent has been obtained, the procedure will take place in the ENT (otolaryngology) clinic. Patient demographic and procedure data will be collected. A parent survey will be completed upon completion of the procedure, but the decision to complete the survey is at the discretion of the parent. If a parent opts not to complete the survey, it will not be considered a protocol deviation.

11.1.3 Additional Information Collection

11.1.3.1 Collection of Videotapes for Patient Tolerability Evaluation

Procedures for a sub-set of patients in the 2-4 and 5-21 year old group who provide consent will be audio and video recorded along with their caregivers (if applicable) to evaluate patient tolerability of the procedure at sites with the capability and resources to perform such recordings. The video will begin on patient arrival to the

procedure room and continue until 3 minutes after the procedure has been completed. These video recordings will be independently reviewed by independent observer(s) to evaluate patients using pre-defined descriptors of 4 different levels of behaviors at 5 different time-points of the procedure: 1) when patient enters room and otoscopy (as applicable), 2) after papoose or swaddling, 3) during wax removal (as applicable), 4) during the Hummingbird procedure and 5) three minutes after procedure is completed.

11.1.3.2 Tympanic Membrane Quadrant

The quadrant of the tympanic membrane where the tube was placed will be recorded (e.g., anterior inferior).

11.1.3.3 Additional Events of Interest

Additional events of interest will also be collected. Definitions are included in Appendix D.

11.1.4 Follow Up

Standard of care data will be collected at the first follow up visit (with audiogram or OAE testing if possible) approximately 3-10 weeks after the procedure. The parent survey will be completed again at the follow up visit, but the decision to complete the survey is at the discretion of the parent. If a parent opts not to complete the survey, it will not be considered a protocol deviation. If a patient does not return for any follow up or the follow up is outside of the expected timeframe, it will not be considered a protocol deviation.

11.2 Study Termination

After the last patient has completed the first follow up visit after the procedure (approximately 3-10 weeks), the study will be terminated. Once monitoring has been completed, the database will be frozen and a clinical report will be prepared and submitted to the IRB.

12.0 ADVERSE EVENTS

Reporting Criteria

All adverse events (AE), both anticipated and unanticipated, will be reported. The event type, treatment, severity, and relationship of the event to the procedure or to the study device will be assessed by the PI performing the procedure. For validation, all AEs will be reviewed by all participating PIs at a clinical site.

Anticipated adverse events and the definitions for serious adverse events are found in Attachment C. Common occurrences (e.g., minor bleeding, purulent discharge) during a tympanostomy procedure are not considered AEs.

13.0 BENEFIT-RISK ANALYSIS

13.1 Benefits

The H-TTS is designed to make an incision and place a tube with one pass through the ear canal and into the tympanic membrane. This has been shown to be a significant reduction in patient trauma compared to the 4-6 passes required for a standard tympanostomy procedure. It also makes the procedure easier for the surgeon particularly in a patient not under general anesthesia. This reduction in trauma is of both benefit to the patient and surgeon because it can reduce the surgical time and the need for anesthetic agents and make placement of a tympanostomy tube under local anesthetic easier for the surgeon.

Additional benefits of using the H-TTS and performance of the procedure in an otolaryngology clinic include: avoiding risks associated with general anesthesia, no NPO restrictions, more cost effective, convenient immediate treatment vs. having to return at a later scheduled date for the procedure (as well as no need for pre- or post-op appointments). The increase cost of both time and money to society of a preoperative visit to primary care prior to general anesthesia is also eliminated.

The position of the American Academy of Otolaryngology – Head and Neck Surgery (AAO-HNS) is that tympanostomy tubes are safe and effective for managing otitis media in children who meet current guidelines for tube insertion. Although insertion of tympanostomy tubes in children is generally accomplished in the operating room under general anesthesia, insertion in the clinic in appropriately selected patients using shared decision making between clinicians and families can be appropriate.

13.2 Risks

Previous clinically studies have demonstrated that the risks for this study are no different from those associated with standard tympanostomy procedures.

Potential risks or discomforts associated with any tympanostomy tube surgery include, but are not limited to, the following: otorrhea, acute tube extrusion, chronic tube extrusion, tube dislocating into the middle ear, tube plugging, bleeding, vertigo, nausea, infection, hearing loss, facial nerve injury.

Older children and adults typically receive ear tubes in a clinic setting using only local anesthetic since they can remain still and tolerate the procedure. In this study, movement will be controlled to prevent motion that could interfere with the procedure while the surgical instruments are in the ears. Except for movement, which will be controlled by the nurse and doctor, the researcher and sponsor are not aware of any risks in this study that are different from normal ear tube procedures in an office setting. Methods to control patient movement in this study are no different than those normally used for children treated in the clinic for a procedure such as removal of a foreign body in the ear or nose or remove cerumen, or to perform such routine procedures as flexible nasopharyngoscopy or flexible laryngoscopy in the clinic.

14.0 PROTOCOL MODIFICATIONS AND DEVIATIONS

The investigator may not modify this protocol without obtaining written concurrence from Preceptis. The investigator, in conjunction with Preceptis, will submit protocol modifications to the IRB as necessary.

Any deviations from this protocol intended to protect the physical well-being of a patient are to be reported to Preceptis and the IRB as soon as possible and no later than five (5) working days after the deviation occurred. Other deviations should be reported according to IRB policies and to Preceptis as soon as possible.

15.0 STUDY MATERIALS

Study materials will be provided by Preceptis. The site will be responsible for the securing, storage, and handling of study materials according to site-specific institutional processes.

16.0 INVESTIGATIONAL DEVICES

For purposes of this study, the H-TTS is considered an investigational device and inventory must be stored in a secure, locked location with limited access. Inventory records must be maintained to document disposition of each device.

17.0 MONITORING PROCEDURES

An employee of Preceptis Medical, Inc., or its designee, will serve as study monitor. At least one monitoring visit will occur prior to conclusion of the study, COVID-19 permitting. Study monitoring activities will include verification of study data to source documents. Monitors may also assume responsibility for communications between the investigator and Preceptis.

Site visits are performed to ensure that the proper medical records are reviewed and that study data is complete and accurate. Database downloads and study documentation will be compared to source documentation and reviewed for accuracy, completeness, and protocol compliance. The following documents will also be monitored:

- Consent documents: Appropriate consent documents must be signed by each patient/parent. These documents will be monitored 100% to ensure they are in compliance.
- IRB: All approvals, adverse events reports, unanticipated adverse device effect reports, protocol deviations, annual reports and other correspondence with the site's IRB must be up to date and on file. These documents will be monitored 100% to ensure they are in compliance.

Site visits will also be used to verify source data, assess the maintenance of records and reports, evaluate progress toward meeting study objectives, and identify any concerns that stem from observations of study management documents. Resolution of concerns and completion of corrective actions will be documented by the study monitor in monitoring reports. At the conclusion of the study, a final monitoring visit will occur to close out the study.

ATTACHMENT A CONSENT FORMS

ATTACHMENT B CASE REPORT FORMS

ATTACHMENT C ADVERSE EVENTS

| Anticipated AE | Definition |
|--|--|
| Acute tube extrusion | During the surgical procedure, a myringotomy incision is completed but the tympanostomy tube will not stay in the tympanic membrane. |
| Tube dislocating into middle ear space and cannot be retrieved | Tube passes completely through the tympanic membrane and falls into the middle ear cavity and is unable to be retrieved (either in the office or in the OR). |

SERIOUS ADVERSE EVENT DEFINITIONS

- 1. Event resulted in death
- 2. Event was life-threatening
- 3. Event required new hospitalization (> 24 hours stay)
- 4. Event required prolonged hospitalization (> additional 24 hours)
- 5. Event resulted in disability or permanent damage (e.g., permanent hearing loss)
- 6. Event required medical or surgical intervention to preclude permanent impairment of a body function, or prevent permanent damage to a body structure, *due to the use of a medical device.*

ATTACHMENT D- Definitions for Additional Events of Interest

| Events | Definition | |
|---|--|--|
| | Infection as defined as: | |
| Infection | Patient has fever > 101 F beyond 24 hours post-surgically (per parent feedback) OR | |
| | Unusual or excessive TM inflammation OR | |
| | Otitis externa | |
| Unintended TM perforation | During the procedure, the surgeon inadvertently creates a perforation in the TM without successfully delivering a tube. | |
| Hearing loss due to damage to | Hearing loss due to procedural damage to the ossicular chain due to the | |
| middle ear structures | tube being placed in the posterior-superior quadrant. | |
| Abrasion of the external auditory canal | Excessive or unusual abrasion to the external auditory canal at time of procedure. | |
| Ear bleeding | Excessive or unusual bleeding in the ear canal or tympanic membrane that requires epinephrine or oxymetazoline at the time of the procedure. | |
| Medialized or partially medialized tube | Ear tube is medialized or partially medialized at follow-up. | |
| Ear Pain | Excessive or unusual ear pain exhibited by the child or reported by the parent or by the child at follow-up. | |
| Lateral displacement of tube | Lateral displacement of tube during deployment | |

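### Attachment D lets parent-reported fever alone count as Infection, with no closing date, ear finding or attribution step, so the infection rate picks up unrelated illness and rises with time to visit

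*Combined protocol and SAP*

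**What the plan says.** Attachment D defines Infection, one of the additional events of interest, by three criteria joined by OR:

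- "Patient has fever > 101 F beyond 24 hours post-surgically (per parent feedback) OR"
- "Unusual or excessive TM inflammation OR"
- "Otitis externa"

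The CRF table in section 11.1 times the form for these events (CRF #5) as "Upon completion of follow up visit", and places that visit about 3-10 weeks after the procedure. Section 11.1.4 adds that if the "follow up is outside of the expected timeframe, it will not be considered a protocol deviation".

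Section 12.0 has the investigator assess each adverse event's relationship to the procedure or device. Neither section 11.1.3.3 nor Attachment D states such a step for the additional events of interest.

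Section 13.2 lists the risks of tube surgery as "otorrhea, acute tube extrusion, chronic tube extrusion, tube dislocating into the middle ear, tube plugging, bleeding, vertigo, nausea, infection, hearing loss, facial nerve injury". Otorrhea and infection are separate items in that list. Otorrhea has no row in Attachment C or D.

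**The concern.** The fever criterion has a start but no end. Because the criteria are alternatives, a parent's report of a fever above the threshold is enough, whatever its cause. A child with a cold and 102 F in week 6 meets the definition as literally written, with a normal ear.

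The period at risk is the interval from the day after the procedure to whenever the family returns. It therefore differs between children by a factor of about three inside the expected window, and by more if a visit falls late. The same true infection risk would give different reported rates depending on scheduling.

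The study is treatment-only (section 3.0), so no control group shows how much fever would have occurred anyway. Section 5.1 calls for summary statistics on all outcome variables, overall and in each age group of 30, and rests study success on a qualitative reading of all the data. An infection rate that mixes procedural infection with ordinary illness would enter that reading. It could suggest a problem that does not exist, or make a real one hard to see.

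**Working it through.** **The plan's own figures.** The documents state no expected infection or fever rate. Section 6.0 gives exact 95% intervals only for delivery adverse events and delivery success. These reproduce with Clopper-Pearson limits at the nearest whole counts: 5/120 gives 1.4-9.5%, 3/60 gives 1.0-13.9%, 114/120 gives 89.4-98.1% and 57/60 gives 86.1-99.0%. They are sound and do not bear on the infection definition.

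**Inputs.**
- Visit at 3 or 10 weeks: sections 11.1 and 11.1.4.
- 60 subjects, 30 per age group: section 6.0.
- Background rate r of fevers above 101 F unrelated to the ear: **assumed**, 0.5 to 6 per child-year, because the documents give none.

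**Formula.** With fevers arising as a Poisson process, the chance that a child without procedural infection has at least one qualifying fever before a visit at w weeks is

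p = 1 - exp(-r × w / 52).

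For example, r = 2 and w = 10 gives 1 - exp(-20/52) = 1 - exp(-0.385) = 31.9%.

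| Assumed fevers per child-year | Flagged, visit at 3 weeks | Flagged, visit at 10 weeks | Ratio |
|---|---|---|---|
| 0.5 | 2.8% (1.7 of 60) | 9.2% (5.5 of 60) | 3.2 |
| 1 | 5.6% (3.4) | 17.5% (10.5) | 3.1 |
| 2 | 10.9% (6.5) | 31.9% (19.2) | 2.9 |
| 4 | 20.6% (12.4) | 53.7% (32.2) | 2.6 |
| 6 | 29.3% (17.6) | 68.5% (41.1) | 2.3 |

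The counts assume that every child is seen at that week, so the two columns are extremes. A real schedule would fall between them unless visits run outside the window.

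**Leaving out the first 24 hours.** Using p = 1 - exp(-r × (days - 1) / 365.25), the range becomes 2.7-28.0% at day 21 and 9.0-67.8% at day 70. The conclusion is the same.

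**Effect of a closing date.** If the fever criterion closed at day 7 (an illustration, not a proposal), the same formula gives 0.8% at r = 0.5 and 9.4% at r = 6, and the result no longer depends on when the visit takes place.

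**The other reading.** If the 24-hour phrase means fever lasting beyond the first day, p is smaller by an amount the documents do not allow one to calculate. The text still sets no latest onset and no ear source, so the dependence on visit timing remains.

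**The case against.** The strongest reply is that the size is entirely assumed. A range of 3% to 68% is too wide to say how much of the infection rate would be background illness. The calculation also supposes that parents recall every fever up to 10 weeks later, and it applies one range of rates to ages 2 through 21. All of this stands. A reader might infer that the infection rate would mostly measure childhood illness, but the documents do not support that; they support only the direction.

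Second, the phrase may be meant as post-operative fever that persists. That is a fair reading and would flag fewer children. It does not supply an end date or an ear source.

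Third, a reader might infer that otorrhea is lost. It is not. Section 13.2 lists it apart from infection, so leaving it out of the Infection definition is consistent. Section 12.0 requires all adverse events to be reported, and its exclusion, "Common occurrences (e.g., minor bleeding, purulent discharge) during a tympanostomy procedure are not considered AEs", covers only discharge at the procedure. Later otorrhea therefore remains reportable; what is missing is a row of its own in the attachments. Two of the three infection criteria are also ear-specific.

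Fourth, a reader might expect the definition to distort a comparison of ages 2-4 with ages 5-21. Section 5.1 analyses the groups separately and plans no such comparison.

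Fifth, the case report forms are not in the text available for review and may already record onset date, criterion met or attribution. If so, the data problem is smaller, but the definition in Attachment D would still need to match.

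Finally, Infection is not one of the two delivery events of main interest, and over-counting works against the device. Both points limit the consequence without making the rate interpretable.

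**Conclusion.** The point holds in a limited form. Applied as written, the definition counts unrelated febrile illness as Infection, and the count rises with time to visit. That follows from the wording and needs no assumed rate.

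The size does need one. Under 0.5-6 background fevers per child-year, a Poisson process, complete parental recall and the literal reading of the 24-hour phrase, roughly 3-29% of children would be flagged at 3 weeks and 9-68% at 10 weeks without any procedural infection. Under the persisting-fever reading the figures are lower by an unknown amount.

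What is affected is the interpretability of one additional safety rate in a study without a control arm. The rates of acute extrusion and displacement into the middle ear, the delivery success rate and the sample size are untouched.

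**What to change.** In Attachment D and on CRF #5:

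1. State whether the 24-hour phrase refers to the onset of fever or to its persistence.
2. Record the fever onset date, if the form does not already.
3. Count fever as Infection only if it begins within a prespecified early post-procedure window chosen by the sponsor, or occurs with a concurrent ear finding.
4. Report the three criteria separately as well as combined.
5. List all other fevers with their onset dates, without counting them.

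Optionally, tabulate post-procedure otorrhea as its own item, separate from Infection. It should not become a fourth criterion, because without an end date it too would grow with time to visit.

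The cost is a reworded definition and one date field, with no new visit or test. There are two drawbacks. A late procedure-related fever without an ear sign would be listed rather than counted. And if the completed 6-24 month cohort used the present definition, which the documents do not say, a changed one would break comparability; in that case the rate under the present definition should be tabulated alongside.
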